# 7.15 Out-Patient Questionnaires

# 7.15.1 McGill Short Form Pain Questionnaire

Subjects will be asked to complete a McGill Short Form Pain Questionnaire for their physical mouth and tooth pain at 1, 2, 3, 7 and 14 days post-procedure and at all Follow-up Visits . This

form should be completed and returned to the clinical site designee at the next study visit or using certified mail or using a pre-paid FedEx envelope.

If the subject is unable to complete one or more outpatient McGill Short Form Pain Questionnaire(s) then the clinical site designee may call the subject and complete the questionnaire(s) themselves based upon responses provided by the subject.

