# 7.15.2 Gracely Descriptor Differential Scale (DDS)

Subjects will be asked to complete a Gracely Descriptor Differential Scale Questionnaire wherein they will be asked to rate the sensation felt in the tooth treated with Sonendo GentleWave System at 1 day post-procedure. This form should be completed and returned to the clinical site designee at the next study visit or using certified mail or using a pre-paid FedEx envelope.

If the subject is unable to complete the outpatient Gracely Descriptor Differential Scale Questionnaire then the clinical site designee may call the subject and complete the questionnaire themselves based upon responses provided by the subject.

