## 7.19 Mail, Telephone and Dentist Contact

If the subject is unable or unwilling to attend all study visits, the subject consents to be called or sent mail by the PI or clinical site designee to provide information about their dental status.

The data provided via telephone contact or mail may include the following:

- 1. Medical and Dental History and Exam
- 2. Medication Regime
- 3. McGill Short Form and/or Numeric Rating Scale

The clinical site designee will follow the Numeric Rating Scale mentioned below or verbally ask questions on the McGill Short Form Pain Questionnaire. When asking the patient to rate their pain per the Numeric Rating Scale, the following question should be asked:

"On a scale of 0 to 10, with 0 being 'no pain' and 10 being the 'most intense pain imaginable', what would you rate the severity of your tooth pain right now"?

4. Adverse Events

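### The day 1 to 14 pain forms have no completion window and no latest date for telephone completion, so a score recalled months later cannot be told from a same-day score

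*Combined protocol and SAP*

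**What the plan says.** Section 7.15.1 asks subjects to report "physical mouth and tooth pain at 1, 2, 3, 7 and 14 days post-procedure". On return it says the "form should be completed and returned to the clinical site designee at the next study visit or using certified mail" or by pre-paid courier envelope. The telephone rule reads: "If the subject is unable to complete one or more outpatient McGill Short Form Pain Questionnaire(s) then the clinical site designee may call the subject". Staff then fill the form in from the answers given.

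Section 7.15.2 applies the same arrangement to the DDS, on which subjects "rate the sensation felt in the tooth treated with Sonendo GentleWave System at 1 day post-procedure". It has the same return routes and the same telephone allowance: "If the subject is unable to complete the outpatient Gracely Descriptor Differential Scale Questionnaire then the clinical site designee may call the subject".

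Section 7.17 places the follow-up visits at 6, 12, 18 and 24 months. Section 7.17.1 gives tolerances for treatment and for those four visits only. The schedule in section 8.0 has columns for days 1, 2, 3, 7 and 14 but prints no tolerance in them, and the questionnaires are the only items marked there. Section 12.1.1 lists separate deviation types for a questionnaire not done and for one done outside its window.

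**The concern.** Acute pain after a root canal changes over days, and the sampling on days 1, 2, 3, 7 and 14 is meant to capture that course. A score carries that information only if it was given on or near its day. As written, a site need not find out that a form is blank until the subject returns at month 6, and staff may then fill it in from what the subject remembers. The text does not say whether the answers should describe the target day or the day of the call, and it does not require the date or mode of completion to be recorded.

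Same-day self-reports and distant recollections taken down by staff could therefore sit under the same day label. Without a date and mode, no sensitivity analysis could reliably separate them. Post-procedure pain is in the study objective (section 1.0) and purpose (section 3.0), the McGill and DDS head the list of secondary endpoints (section 3.3), and reduced pain is the first potential benefit named in section 11.0. The study has a single arm, so there is no concurrent group in which such measurement error might balance out.

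**Working it through.** The plan states no figure for this point, so there is none to reproduce. The check sets the rules side by side and then does date arithmetic.

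**Rules compared**

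| Question | Days 1 to 14 | Months 6 to 24 |
|---|---|---|
| Due day stated? | Yes (7.15.1, 7.15.2, 8.0) | Yes (7.17) |
| Tolerance stated? | No (7.17.1, 8.0) | Yes, ±14 to ±45 days (7.17.1) |
| Latest date for return? | None; next study visit is allowed | Not applicable |
| Latest date for telephone completion? | None | Not examined here |
| Can the out-of-window deviation be applied? | Not consistently, as there is no window | Yes |

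The two-week limit for completing CRFs in section 14.0 runs from a study visit, so it does not bound forms due between visits.

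**Recall lag if a blank form is filled in at the month 6 visit**

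Inputs: month 6 taken as 365.25 / 2 = 182.6 days; visit window w = −14 to +14 days (7.17.1); form day d (7.15.1, 7.15.2).

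Lag = 182.6 + w − d

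| Form day | w = −14 | w = 0 | w = +14 |
|---|---|---|---|
| 1 | 167.6 | 181.6 | 195.6 |
| 2 | 166.6 | 180.6 | 194.6 |
| 3 | 165.6 | 179.6 | 193.6 |
| 7 | 161.6 | 175.6 | 189.6 |
| 14 | 154.6 | 168.6 | 182.6 |

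The range is about 155 to 196 days, or 5.1 to 6.4 months.

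**Number of forms open to this**

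Each subject has 5 McGill forms + 1 DDS form = 6 outpatient forms. Section 13.1 gives 108 subjects, of whom about 86 are evaluable: 6 × 86 = 516 and 6 × 108 = 648. The documents give no rate of missed forms. If 10% to 20% were missed (an assumption), that is 52 to 103 forms on 86 subjects, or 65 to 130 on 108. These are ceilings. They require every missed form to be filled in late, and the 108 includes Treatment Incomplete subjects, on whom section 7.10 stops data collection.

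**The case against.** The strongest reply has four parts.

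- **Late return is not late completion.** A form filled in on day 1 and handed over at month 6 involves no recall, and the telephone route is open only when the subject was unable to complete the form. This stands. The risk is confined to forms filled in late, by the subject or by telephone.
- **Earlier contact is possible.** A Second Procedure Visit (7.9), an Unscheduled Visit (7.18) or collection of the crown date (7.16) could reveal a blank form sooner. This also stands, and it makes the lag above a worst case. None of these contacts is required to check the forms.
- **The protocol does recognise late questionnaires.** A reader might infer that a day 1 score obtained at month 6 counts as on time. The documents do not say so: section 12.1.1 lists an out-of-window deviation for questionnaires. Where the protocol waives deviations, as for independent PAI scoring, it says so, and it gives no such waiver here. What remains is narrower. With no window for days 1 to 14, one site could treat any form not done on the exact day as a deviation, and another could treat none as one.
- **The bias has no established direction.** A reader might infer that recall favours low pain. No passage supports that. Loss of comparability does not depend on the direction.

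A reader might also infer from section 7.19, which lists "McGill Short Form and/or Numeric Rating Scale" among the telephone data, that a 0 to 10 rating of current pain replaces a McGill score. That section concerns missed study visits, which section 7.17 places at months 6 to 24, and it does not say the rating is scored as a McGill value. It is a side issue here.

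**Conclusion.** The gap is real but limited. The protocol sets due days for the early pain forms and then gives no window, no latest date for telephone completion and no requirement to record when or how a form was completed. Following its rules can yield a day 1 to 14 score recalled about 155 to 196 days later that cannot be told apart from a same-day score.

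That range assumes a blank form is found and filled in at an in-window month 6 visit, with no earlier contact about the forms. How often this would happen cannot be known from the documents. The McGill and DDS summaries are affected. The 24-month healing endpoint and its sample size are not. The change is worth making because it is cheap and because the loss cannot be repaired once the data are collected.

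**What to change.** 1. **Return (7.15.1, 7.15.2).** Have all day 1 to 14 forms sent back in the pre-paid envelope shortly after day 14, and remove return at the next study visit for these forms.
2. **Windows (7.17.1, 8.0).** Define a short completion window for each day and apply it to telephone completion too. For example: the due day or the day after for days 1 to 3, and within 2 days for days 7 and 14. These limits are a suggestion and do not come from the documents. Once set, they give the deviation type in section 12.1.1 something to refer to.
3. **Date and mode.** Record on every form when it was completed and whether by the subject or by telephone. This is needed alongside item 1, because an envelope sent after day 14 does not stop a subject from filling in all the forms in one sitting.
4. **Analysis (13.7).** Treat out-of-window forms as missing in the main pain summaries and do not carry an earlier score forward to fill them. Section 13.7 names both last observation carried forward and complete-case analysis. Under the first, a missing day 1 McGill score could be replaced by the pre-procedure baseline score.
5. **Section 7.19 (secondary).** If a 0 to 10 rating is taken at a missed follow-up visit, report it separately from McGill scores.

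The cost is protocol wording and, if the forms lack them, fields for completion date and mode; the CRFs are not in the documents. The envelope and telephone routes already exist. A site wishing to use the telephone route will have to check with subjects around the due days. The downside is that some values that would have been collected late become missing.

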# 7.15.2 Gracely Descriptor Differential Scale (DDS)

Subjects will be asked to complete a Gracely Descriptor Differential Scale Questionnaire wherein they will be asked to rate the sensation felt in the tooth treated with Sonendo GentleWave System at 1 day post-procedure. This form should be completed and returned to the clinical site designee at the next study visit or using certified mail or using a pre-paid FedEx envelope.

If the subject is unable to complete the outpatient Gracely Descriptor Differential Scale Questionnaire then the clinical site designee may call the subject and complete the questionnaire themselves based upon responses provided by the subject.

# 7.16 Crown Placement

Subjects enrolled in the study should obtain a permanent crown per standard of care. It is recommended that crown placement should occur within six weeks of the root canal therapy procedure per standard of care. For the protocol, final crown placement date will be the date CRC obtains from the subject and/or GP and/or the Investigator.

Pain and tenderness to percussion, palpation, ill-fitting margins, open margins, high occlusal contact points with the opposing teeth or any other restoration related issues after crown placement experienced by the patient or reported by the PI and/or SD and/or Crown Placement dentist, will not be considered an adverse event but will be documented.

# 7.17 Follow-Up Study Visits

The study follow-up visits will occur 6, 12, 18, and 24 months post-procedure. In addition, subjects may be requested to attend Follow-up Visits once a year after the twenty-four month follow-up for up to ten years.

# 7.17.1 Follow-Up Study Visit Windows

The visit windows are as follows:

- Treatment: Within seven (+7) days of the baseline visit
- 6 Month Visit: Plus or minus fourteen (±14) days.
- 12 Month Visit: Plus or minus thirty (±30) days
- 18 Month Visit: Plus or minus thirty (±30) days
- 24 Month Visit: Plus or minus forty-five (±45) days

# 7.17.2 Follow-Up Visit Evaluations and Assessments

These study follow-up visits will occur at the clinical site and the following assessments will occur according to standard of care at each visit:

- 1. Medication Regime: Only prescribed herbal or over the counter systemic antibiotics, analgesics, and anti-inflammatory medications taken during the duration of the study (24 months post procedure) and the prior three months will be documented for this study.
- 2. McGill Short Form Pain Questionnaire: The McGill Pain Questionnaire (MPQ) is one of the most widely used tests for the measurement of pain. It provides information on sensory, affective, and evaluative dimensions of pain experience and is capable of discriminating among different pain problems.
- 3. Diagnostic Radiographic Analysis: Periapical (PA) Parallel Radiograph, showing the periapical region surrounding the subject tooth should be collected for each visit. Additional radiographs completed as necessary by the PI will be collected for the study.
- 4. Periapical Index (PAI) Score analyzed by independent reviewer

Up to three (3) independent reviews will be provided radiographs in order to complete the PAI scoring. Independent reviewers will be blinded to the site, subject, and visit when completing the PAI score. This is being done to eliminate bias.

- Score of 1: Normal
- Score of 2: Small changes in bone structure
- Score of 3: Changes in bone structure with some mineral loss (bone loss)
- Score of 4: Periodontitis with well-defined radiolucent area (apical periodontitis)
- Score of 5: Severe Periodontitis with exacerbating features (apical periodontitis)

Note: A Protocol Deviation CRF will not be completed if PAI score was not completed by independent reviewer for a particular visit. In addition there is no defined study window for completion of PAI scoring by independent reviewer.

- 5. Dental Cone Beam Computed Tomography (CBCT) at 12 and 24 months and additional as required by the PI.
- 6. Intra-Oral Examination including, but not limited to:
  - a. Tooth Number: Based on the Universal Tooth Numbering System (1-32)
  - b. Subject Tooth Assessments including:
    - i. Probing Pocket Depth: The distance between the height of the free gingival margin and the height of attachment apparatuses below (bone, cementum, and periodontal ligament). Using a calibrated periodontal probe, the periodontal pocket depth should be recorded on the mesial, middle, and distal aspects of both the buccal and lingual sides of the tooth
    - ii. Mobility

- None: No distinguishable sign of movement.
- Class I: The first distinguishable sign of movement greater than normal.
- Class II: Horizontal tooth movement no greater than 1 mm.
- Class III: Horizontal tooth movement greater than 1 mm, with or without the visualization of rotation or vertical depressability.
- Any mobility other than none should be considered abnormal.
- iii. Swelling: This assessment includes the type and location of swelling.
- iv. Soft Tissue Lesions: This assessment includes the lesion presence, color and size where applicable. This assessment shall also include ulcerations and fistula/sinus tract.
- v. Root Resorption
- vi. Furcation Involvement/Furcation Defect
  - Class I: The furcation can be probed, but not to a significant depth.
  - Class II: The furcation can be entered into but cannot be probed completely through to the opposite side.
  - Class III: The furcation can be probed completely through and through.
  - Class IV: The furcation can be probed through and through, and recession reveals a visible furcation.
- 7. Endodontic Assessments including:
  - a. Periradicular Tests (Percussion and Palpation)
    - None (-): No discomfort at all.
    - Mild (+): Little discomfort, but may be noticeable by the patient.
    - Moderate (++): Some noticeable discomfort.
    - Severe (+++): Definitive discomfort.
  - b. Periradicular Diagnosis:
    - Normal Apical Tissue: Teeth with normal periradicular tissues that are not sensitive to percussion or palpation testing. The lamina dura surrounding the root is intact, and the periodontal ligament space is uniform.
    - Symptomatic Apical Periodontitis: Inflammation, usually of the apical periodontium, producing clinical symptoms including a painful response to biting and/or percussion or palpation. It might or might not be associated with an apical radiolucent area.
    - Asymptomatic Apical Periodontitis: Inflammation and destruction of apical periodontium that is of pulpal origin, appears as an apical radiolucent area, and does not produce clinical symptoms.

- Acute Apical Abscess: An inflammatory reaction to pulpal infection and necrosis characterized by rapid onset, spontaneous pain, tenderness of the tooth to pressure, pus formation, and swelling of associated tissues.
- Chronic Apical Abscess: An inflammatory reaction to pulpal infection and necrosis characterized by gradual onset, little or no discomfort, and the intermittent discharge of pus through an associated sinus tract.
- Condensing Osteitis: Diffuse radiopaque lesion representing a localized bony reaction to a low-grade inflammatory stimulus, usually seen at apex of tooth
- 8. Adverse Events (see Section 10.0 Adverse Event).

After assessments are completed, the patient may be prescribed medication(s) for pain management according to standard of care procedures. If analgesic medications need to be provided to the patient in order to complete one or more of the assessments, the assessments that require a pain response (i.e. cold test, percussion and palpation) should be completed prior to providing this medication.

All redacted source documentation with PI signature should be provided to the Sponsor for filing after each study visit. If changes are made to the source documents after PI signature, the updated source documents should be provided to the Sponsor for filing.

In addition, the clinical site designee will report all significant findings at Follow-Up Visits to the Sponsor either via email or by sending redacted source documentation.

Subjects should be evaluated to determine if the subject tooth remains functional. If the subject tooth is or still requires healing, the subject should be evaluated closely. If the subject has clinical symptoms or signs after the twelve month follow-up, the PI should follow standard endodontic care, as applicable. All such care should be documented accordingly for the study.

# 7.18 Unscheduled Visits

Apart from the scheduled study visits, if the subject returns to the PI for a suspected adverse event (AE), the PI may perform tests and request additional information about what the subject is experiencing. Only those assessments that the PI deems as necessary for assessment of a possible AE will be collected. Assessments that are not completed during the Unscheduled Visit will not be considered as Protocol Deviations. The information collected at this visit will be recorded on appropriate Case Report Forms. An Unscheduled Visit will not be completed unless an AE is suspected.

All redacted source documentation with PI signature should be provided to the Sponsor for filing after each study visit. If changes are made to the source documents after PI signature, the updated source documents should be provided to the Sponsor for filing.

## 7.19 Mail, Telephone and Dentist Contact

If the subject is unable or unwilling to attend all study visits, the subject consents to be called or sent mail by the PI or clinical site designee to provide information about their dental status.

The data provided via telephone contact or mail may include the following:

- 1. Medical and Dental History and Exam
- 2. Medication Regime
- 3. McGill Short Form and/or Numeric Rating Scale

The clinical site designee will follow the Numeric Rating Scale mentioned below or verbally ask questions on the McGill Short Form Pain Questionnaire. When asking the patient to rate their pain per the Numeric Rating Scale, the following question should be asked:

"On a scale of 0 to 10, with 0 being 'no pain' and 10 being the 'most intense pain imaginable', what would you rate the severity of your tooth pain right now"?

4. Adverse Events

# 7.20 Subject Completion

Subjects are considered to have completed the study when they have completed the twentyfour (24) month follow-up examination. Subjects may be requested to have an in person or telephone follow-up visit every year after the twenty-four (24) month visit for up to ten (10) years.

Sonendo, Inc. 1 August 2014

#### **8.0 SCHEDULE OF VISITS**

Description	Screening	Baseline	Procedure  (+7 ds)	Post- Operative	1 day	2 days	3 days	7 days	14 days	6 mo. (± 14ds)	12 mo. (± 30ds)	18 mo. (± 30ds)	24 mo.² (± 45ds)	Unsched uled Visits
Screening Form by Screening Dentist or Pl	x													VISIUS
Images of Smile & Oclussal Surface	х													
X-Rays (Periapical) 	x	x	x	х						х	х	х	х	As needed
Medical and Dental History	х	x								х	x	х	х	As needed
Medication Regimen Review	x	x								х	х	х	х	As needed
Informed Consent		x								As needed	As needed	As needed	As needed	As needed
СВСТ		X, if applicable		X, if applicable							X, if applicable		X, if applicab le	As needed
McGill Short Form		х			x	х	х	x	х	х	x	х	х	As needed
Gracely DDS		x		x	x									
Periapical Index Score		x								х	х	х	х	As needed
General Dental and Endodontic Assessments		x								х	x	х	x	As needed
Sonendo GentleWave Treatment			x											
Root Canal Therapy			х											
Intra Assessments and Evaluations			x											
Post Operative Assessments and Evaluations				х										
Patient Satisfaction Survey				х										
AAE Case Difficulty Assessment				x										
Adverse Event Assessment			x	x						х	x	х	х	As needed

- 1. The procedure must be completed within seven days (7) of the baseline visit. For any treatment not completed within seven days of the baseline, the baseline assessments must be completed again within the time frame indicated. In addition, if a subject must return to the clinical site for completion of a procedure, as indicated in *Section 7.9 Second Procedure* Visit, this must also occur within seven days of the baseline.
- 2. Subjects may be asked to have a follow-up visit every year after the twenty-four (24) month visit for up to ten (10) years.
- 3. Only PA Parallel radiographs will be obtained.

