#### **3.1** Primary Effectiveness Endpoints

Subject teeth in the Treatment Complete cohort that are healed or are healing at the twentyfour month Follow-up Visit.

Healed is defined by absence of a radiographic indication of apical periodontitis (PAI <3) and absence of clinical signs and symptoms.

Healing is defined by a reduction of radiolucency (if radiolucency is present at Baseline) and/or reduction of clinical signs and symptoms (if clinical signs and symptoms are present at Baseline)

Secondary analysis will be performed after all Treatment Complete subjects have completed the 12 month Follow-up Visit.

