# 7.4.5 Baseline Exam Re-Assessment

For most patients, the Baseline and Procedure Visits will be on the same day. The patient and/or PI may choose to have the Procedure Visit occur on a day separate than that of the Baseline Visit.

If the Procedure Visit is not on the same day as the Baseline Visit, the Procedure must occur within seven (7) days. If the Procedure Visit is not completed within seven (7) days of the Baseline Visit, the Baseline Exam results are no longer valid and must therefore be repeated and captured on a new source document. Only data captured on the final Baseline Visit will be used for data analysis and will be monitored. All assessments listed under *Section 7.4.4 Baseline Exam* need to be repeated if the Procedure Visit is not completed within seven (7) days of the Baseline Visit.

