## 7.8 Control of Bleeding

Bleeding and control of bleeding during any RCT is expected and is considered standard of care. Bleeding is typically controlled through a combination of paper point usage, waiting for the bleeding to stop, starting the cone fit process and usage of intra-canal medications. If bleeding cannot be controlled and prevents the System from treating the tooth, the PI should pack the tooth with calcium hydroxide (Ca(OH)2) and restore the tooth with temporary material until the patient can be scheduled for a Second Procedure Visit according to standard of care.

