## 7.9 Second Procedure Visit

The Sonendo GentleWave treatment may be completed on a subsequent visit, a Second Procedure Visit. The Second Procedure Visit can be scheduled according to standard of care.

At this visit, the PI should remove the  $Ca(OH)_2$  with the Sonendo GentleWave System. Use of files or irrigation to remove  $Ca(OH)_2$  is not allowed for the study.

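### The second-procedure-visit timing rules conflict, and read literally they let an examination made after treatment has begun become the analysis Baseline for subjects who finish after day 7

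*Combined protocol and SAP*

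**What the plan says.** **Timing of the second visit.** Section 7.9: "The Second Procedure Visit can be scheduled according to standard of care". Section 7.8, on bleeding that stops the device from treating the tooth, has the tooth packed and temporised "until the patient can be scheduled for a Second Procedure Visit according to standard of care". Neither sets a day limit. Footnote 1 to the schedule in Section 8.0 cites Section 7.9 and says of the return visit that "this must also occur within seven days of the baseline". Section 7.17.1 gives the treatment window as "Treatment: Within seven (+7) days of the baseline visit" and does not mention a second visit.

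**Repeating the baseline.** Footnote 1: "For any treatment not completed within seven days of the baseline, the baseline assessments must be completed again within the time frame indicated". Section 7.4.5: "If the Procedure Visit is not completed within seven (7) days of the Baseline Visit, the Baseline Exam results are no longer valid". It then requires every baseline assessment to be repeated on a new source document and adds: "Only data captured on the final Baseline Visit will be used for data analysis and will be monitored".

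**Use of the baseline.** Section 3.1: "Healing is defined by a reduction of radiolucency (if radiolucency is present at Baseline) and/or reduction of clinical signs and symptoms", the latter again only if present at Baseline. Healed, in the same section, is a status at 24 months (PAI below 3, no clinical signs or symptoms) and makes no reference to Baseline.

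**Who is analysed.** The Synopsis definition of Treatment Complete and the Efficacy Evaluable population in Section 13.2 require full device treatment in at most two visits. Neither has a seven-day condition.

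**The concern.** A site that follows Sections 7.8 and 7.9 can breach footnote 1 without knowing it. The statistical consequence lies in what happens next. If a subject's treatment begins at the first visit and is finished after day 7, footnote 1 calls for a new set of baseline assessments and Section 7.4.5 makes that set the only one analysed and monitored. By then the tooth has been opened and possibly shaped, treated in part by the device, or packed with calcium hydroxide.

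Healing asks whether something present at Baseline has been reduced. If symptoms eased after the first visit, the new baseline no longer shows them and a genuine reduction cannot be credited. If the first visit provoked symptoms, the new baseline records them, and their later resolution can be counted as Healing. Either way the responder status of a tooth in the primary analysis could depend on when its second visit was booked.

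**Working it through.** **1. The plan's own figure.** Section 13.1 has 108 enrolled, 20% attrition, 86 evaluable, 85% against a 70% null, and a two-sided binomial test at 5%.
- 108 × 0.80 = 86.4, so 86.
- Exact binomial, n = 86: the smallest count with upper tail at or below 0.025 under 70% is 69 (upper tail 0.0223). Power at 85% is P(X ≥ 69) = 91.4%.

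The stated power of about 90% is reproduced and is not in dispute. It serves only to set the scale below.

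**2. Timing passages side by side.**

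| Place | Limit on the second visit |
|---|---|
| 7.8 | Standard of care |
| 7.9 | Standard of care |
| 8.0, footnote 1 | Seven days from baseline |
| 7.17.1 | Seven days for treatment; second visit not mentioned |

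Footnote 1 also gives two answers for late completion: the second visit must not be late, yet treatment not completed by day 7 leads to a repeated baseline.

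**3. Following one subject through the text.**
- Day 0: Baseline Exam, then access, shaping and perhaps some device treatment. Section 7.13 defines a device end time for a first visit that needs a second, so a partial device treatment is foreseen.
- Second visit after day 7, as Sections 7.8 and 7.9 permit.
- Footnote 1: treatment was not completed by day 7, so baseline is repeated. Its trigger is completion, not start.
- Section 7.4.5: only the final Baseline Visit is analysed.
- Synopsis and Section 13.2: two visits, full treatment, so the subject is Efficacy Evaluable.
- Section 13 has no definition of Baseline that would override this.

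**4. Which outcomes are exposed.**
- Healed at 24 months: success under either baseline.
- Not Healed at 24 months: success depends on Healing, and so on which baseline is used.

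**5. Scale.**
- One tooth: 1/86 = 1.2 percentage points.
- Under the Section 13.1 test, 69/86 has an exact 95% lower limit of 70.25% (two-sided p = 0.045); 68/86 has 68.95% (p = 0.077). One tooth could matter near that boundary.
- The share of subjects needing a second visit is not stated. If it were 5% to 15% (assumption), that is 0.05 × 86 = 4.3 to 0.15 × 86 = 12.9, or about 4 to 13 evaluable subjects. This is a ceiling under that assumption: only those finishing after day 7 could be re-baselined, and of these only teeth not Healed at 24 months could change status.

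**The case against.** The strongest reply is that re-baselining was meant only for a procedure that has not started. Section 7.4.5 speaks of a Procedure Visit held on a different day from Baseline; Second Procedure Visit is a separate term that it does not use. Section 7.4.4 places the baseline assessments before the procedure, and the set to be repeated includes a cold test and a pulp diagnosis, which suit an untreated tooth. In footnote 1 the sentence on the second visit follows the re-baseline sentence and carries no re-baseline clause of its own. A late second visit could instead be handled as a minor, out-of-window deviation under Section 12.0. This is plausible as intent, but footnote 1 still says any treatment not completed and makes no exception for treatment begun. Intent that is not written down does not bind a site or a programmer.

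On timing, it can be said that Section 7.9 is permissive and footnote 1 adds an outer limit, so both can be met together. That is true, but a reader of Sections 7.8 and 7.9 alone would not learn of the limit.

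Several stronger readings are tempting and not supported:
- That every two-visit subject carries a wrong baseline. Only completion after day 7 triggers the rule, and Section 7.4.5 expects Baseline and Procedure on the same day for most patients, which leaves them the full seven days.
- That the pain outcomes are changes from Baseline. Section 3.3 only lists the instruments, and Section 13.5 specifies no such analysis.
- That 69 of 86 is the trial's pass line. It follows from the test in Section 13.1; Section 13.4 prescribes a proportion with an exact interval and states no success rule.
- That the device has always been used in part by then. Section 7.8 describes bleeding that prevents the device from treating the tooth.

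**Conclusion.** The point holds in a limited form. The timing passages are inconsistent and must be reconciled. Read as written, footnote 1 with Section 7.4.5 substitutes an examination made after treatment has begun for the pre-treatment one, in subjects who start treatment and finish after day 7 and who remain in the primary analysis.

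A reader might infer that the primary endpoint as a whole is corrupted. The documents do not support that: the exposure is confined to the Healing part, and to any secondary summary that is later referred to baseline. How many subjects are affected cannot be derived, and the direction of bias is not fixed, since relief and flare-up after the first visit push opposite ways. Signs and symptoms are more likely to be affected than radiolucency over so short an interval, but that is a judgement and not a figure from the plan.

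The conclusion rests on the literal reading of footnote 1. It merits correction because the rule can misclassify a primary outcome and wording alone cures it.

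**What to change.** 1. Reconcile Sections 7.4.5, 7.8, 7.9, 7.17.1 and footnote 1 on the timing of the Second Procedure Visit, so that each states or cross-refers to the same rule. Which interval applies is for the sponsor and investigators.
2. In Section 7.4.5, footnote 1 and Section 13 (and the statistical analysis plan that Section 13.0 refers to), state that:
   - the analysis Baseline is the last complete Baseline Exam before the first Procedure Visit begins, that is, before access and shaping;
   - the repeat-baseline rule applies only when the procedure has not started;
   - no examination made after treatment has begun replaces that Baseline, and the pre-treatment examination is kept and monitored.

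Placement of LuxaBite or the Tooth Cap should not be the anchor. Under Sections 7.5.2 to 7.6 it comes after access and shaping, so an examination on an already opened tooth would still qualify.

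The cost is a wording change in five places and one analysis definition. No sample size, visit or assessment is added. The change is best made before data are locked, because under the present text a superseded pre-treatment examination would go unmonitored.
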